10.4.7 Mean Change in mean Daily Dose of Iron Chelation Therapy

The ICT mean daily dose summary will be provided for subjects who did not change ICT drug from baseline to post-baseline and only one ICT drug has been used. Descriptive statistics for mean daily dose will be summarized at baseline and the post-baseline visit for each ICT drug. The baseline mean daily dose will be calculated using the ICT dosage during the 24 weeks on or prior to first study drug treatment and the post-baseline mean daily dose is calculated during the last 24 weeks of the 48-week double-blind treatment period or the last 24 weeks of the study treatment for early discontinued subjects.

The same descriptive statistic summary for baseline and post-baseline ICT drug mean daily dose will be provided for subjects in each baseline liver iron content category (<3 ; ≥ 3 - ≤ 5 ; >5 - ≤ 7 ; >7 - ≤ 15 ; >15 mg/g dry weight).

The change from baseline in mean daily dose at post-baseline will be analyzed using an ANCOVA model with treatment group, randomization stratification factor(s) and baseline ICT mean daily dose as covariates based on the ITT population for subjects who did not change ICT drug from baseline to post-baseline and only one ICT drug has been used.

A summary showing the number and percentage of subjects who took monotherapy (i.e., only one ICT drug) vs. combo therapy (i.e., more than one ICT drug) at the 24-week baseline period and post-baseline period will be provided.

Bar plot will be provided for percent of subjects who took each ICT drug at baseline and postbaseline for subjects who did not change ICT drug from baseline to post-baseline and only one ICT drug has been used. A similar bar plot will be provided for percent of subjects who took monotherapy or combo therapy at baseline and post-baseline.

10.4.8 LIC / ICT: Responder Analysis at Week 24 and Week 48

There are 3 scheduled LIC measurements for each subject: baseline, Weeks 24 and 48. For subjects who discontinued before 48 weeks, the LIC and ICT data may be collected in the PTFP. The value of LIC will be either the value collected from eCRF or the value derived from T2* (see section 10.4.10 for further details). ICT daily dosing data will be collected at every visit during the study. Baseline ICT dose is based on medical history over 24 weeks prior to Dose 1 Day 1.

At Week 24, a LIC/ICT responder will be defined as one of the following:

- Baseline LIC (by MRI) ≥ 3 mg/g dw: $\geq 20\%$ reduction in LIC, OR, $\geq 33\%$ decrease in ICT daily dose
- Baseline LIC < 3 mg/g dw: no increase in LIC > 1 mg/g dw AND not starting treatment with ICT or no increase in ICT daily dose $\geq 33\%$, if on ICT at baseline

CMH test will be performed with treatment group, baseline ICT use (Yes, No) and randomization stratification factors as strata to compare the luspatercept and placebo groups at 2-sided 0.05 level; the corresponding 95% confidence interval for odds ratio will also be calculated.

The subgroup analyses will be performed as described in Section 10.5.

10.4.9 Serum Ferritin: Mean Change from Baseline at Week 24 and Week 48

Descriptive statistics for serum ferritin level will be summarized at baseline, at Week 24 and Week 48 of the 48-week DBTP. The baseline mean serum ferritin is measured during the 24 weeks prior to the first dose and the post-baseline mean serum ferritin is calculated during the last 24 weeks of the 48-week double-blind treatment period or the last 24 weeks of the study treatment for early discontinued subjects. Change from baseline will be summarized at Week 24 and Week 48.

The change from baseline in serum ferritin at Week 24 and Week 48 will be analyzed using an ANCOVA method with treatment group and randomization stratification factor(s) in the model and baseline Serum Ferritin as the covariate. If the normality assumption is significantly deviated, the nonparametric Wilcoxon rank-sum test will be used instead. Mean change at Week 48 will be analyzed similarly.

All the serum ferritin data will be presented in a listing.

10.4.10 Liver Iron Concentration: Mean Change from Baseline at Weeks 24 and 48

LIC mean change from baseline at Week 24 will be summarized descriptively and analyzed using ANCOVA method with treatment group and randomization stratification factor(s) in the model and baseline LIC as covariates.

LIC mean change from Baseline at Week 48 will be analyzed similarly.

The value of LIC will be either the value collected from eCRF or the value derived from T2*, R2* or R2 parameter depending on which techniques and software were used for MRI LIC acquisition and post-processing. The LIC value will be derived as below:

Technique	Site number	Derivation source	Alternative derivation if still missing
T2*/R2*	██████████	$0.0254 * (R2^*) + 0.2$	$25.4/T2^* + 0.2$ If both R2* and T2* are missing, LIC from eCRF will be used
T2*/R2*	██████████	$25.4/T2^* + 0.2$	If both T2* and R2* are missing, LIC from eCRF will be used
T2*/R2*	██████████	$31.94 * (T2^*)^{-1.014}$	$0.029*(R2^*)^{1.014}$ If both T2* and R2* are missing, LIC from eCRF will be used
Ferriscan R2	██████████	Reported LIC from CRF	$(29.75 - \text{SQRT}(900.7 - 2.283 * \text{EXP}((-0.19043 + 1.016385 * \ln(R2)) / 0.983615)))^{1.4265}$

The derived LIC value will be used for analysis. If a subject has any LIC value > 43, the subject's LIC value will be excluded from analysis. Note that, subjects with LIC value > 43 are not excluded from the LIC baseline summary and efficacy subgroup analysis by LIC categories.

Descriptive statistics for LIC measurements and change from baseline will be summarized at week 24/48. The 24/48-week LIC change from baseline will be analyzed using ANCOVA model and randomization stratification factor(s) in the model and baseline LIC as covariates. Additionally, a shift table representing the shift from the baseline to week 24/48 category (<3 ; ≥ 3 - ≤ 5 ; >5 - ≤ 7 ; >7 - ≤ 15 ; >15 mg/g dry weight) will be provided for LIC. A subject will have maximum two post-baseline LIC assessments (including “unscheduled”) during the 48 weeks double-blinded treatment period per protocol. The assessment will be counted as the closest visit (“Week 24” or “Week 48”) based on its actual assessment date. This logic will be used in model based summary, change from baseline summary and the shift table summary.

Additionally, bar plot will be provided for baseline, week 24 and week 48 LIC categories (<3 ; ≥ 3 - ≤ 5 ; >5 - ≤ 7 ; >7 - ≤ 15 ; >15 mg/g dry weight). Percent of subjects within each category will be displayed by treatment group. All the LIC data will be presented in a listing.

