There are 3 scheduled LIC measurements for each subject: baseline, Weeks 24 and 48. For subjects who discontinued before 48 weeks the LIC and ICT data may be collected in the PTFP.

ICT daily dosing data will be collected during the study.

At Week 24 or Week 48, a LIC/ICT responder will be defined as one of the following:

- Baseline LIC (by MRI) ≥ 3 mg/g dw: $\geq 20\%$ reduction in LIC, OR, $\geq 33\%$ decrease in ICT daily dose
- Baseline LIC < 3 mg/g dw: no increase in LIC > 1 mg/g dw AND not starting treatment with ICT or no increase in ICT daily dose $\geq 33\%$, if on ICT at baseline

CMH test will be performed with baseline ICT use (Yes, No) and randomization stratification factor(s) as the strata adjusted to compare the luspatercept and placebo groups at 2-sided 0.05 level; the corresponding 95% confidence interval for odds ratio will also be calculated.

9.6.3.9. Serum Ferritin: Mean Change from Baseline at Week 24 and Week 48

Serum ferritin change from baseline at Week 24 will be analyzed using ANCOVA method with treatment group and randomization stratification factor(s) in the model and baseline Serum ferritin as the covariate.

If the normality assumption is significantly deviated, the nonparametric Wilcoxon rank-sum test will be used instead.

Mean change at week 48 will be analyzed similarly.

9.6.3.10. Liver Iron Concentration: Mean Change from Baseline at Weeks 24 and 48

LIC mean change from baseline will be analyzed using ANCOVA method with treatment group and randomization stratification factor(s) in the model and baseline Liver Iron Concentration as the covariate.

LIC mean change from Baseline at Week 48 will be analyzed similarly.

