4.1.1. Screening Period

Upon giving written informed consent, the subject will enter the Screening Period to determine eligibility. The Screening Period is to last up to 4 weeks with an administrative window of + 3 days to allow all laboratory results to be available at site for evaluating the subject's eligibility. Re-screening is allowed and a new subject ID number will be assigned. Subjects will be stratified at the time of randomization based on baseline hemoglobin level and baseline NTDT-PRO tiredness and weakness (T/W) score.

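### The LIC and serum ferritin change models leave out baseline chelation use; adding it is a near-free precision gain of unknown size on secondary endpoints

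*SAP*

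**What the plan says.** For LIC, SAP 10.4.10 first says that the change at Week 24 will be "analyzed using ANCOVA method with treatment group and randomization stratification factor(s) in the model and baseline LIC as covariates", and then repeats the model: "The 24/48-week LIC change from baseline will be analyzed using ANCOVA model and randomization stratification factor(s) in the model and baseline LIC as covariates". Protocol 9.6.3.10 agrees: "LIC mean change from baseline will be analyzed using ANCOVA method with treatment group and randomization stratification factor(s) in the model", with baseline LIC as the covariate.

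For ferritin, SAP 10.4.9 prescribes an "ANCOVA method with treatment group and randomization stratification factor(s) in the model and baseline Serum Ferritin as the covariate", and Protocol 9.6.3.9 matches it: "Serum ferritin change from baseline at Week 24 will be analyzed using ANCOVA method with treatment group and randomization stratification factor(s) in the model". SAP 10.4.9 adds a fallback: "If the normality assumption is significantly deviated, the nonparametric Wilcoxon rank-sum test will be used instead".

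The randomisation factors in these models are the two in SAP 4.1.1 and 4.3. Subjects are stratified "based on baseline hemoglobin level and baseline NTDT-PRO tiredness and weakness (T/W) score". Chelation is not among them, and it is not one of the ten subgroups in SAP 10.5.

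Baseline ICT use does appear in the LIC/ICT responder analysis of SAP 10.4.8: "CMH test will be performed with treatment group, baseline ICT use (Yes, No) and randomization stratification factors as strata". Protocol 9.6.3.8 has the same stratum. The 24-week ICT history is collected under Protocol 3.1.1 and is the basis of the baseline ICT dose in SAP 10.4.8.

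**The concern.** The trial enrols subjects both on and off chelation. Chelating agents are permitted in both arms (Protocol 3.1.2), and exclusion criterion 11 requires those already on ICT at consent to have started at least 24 weeks before the predicted randomisation date. Chelation is given to remove iron, so whether a subject is on it at baseline plausibly predicts how LIC and ferritin move over 24 and 48 weeks. Baseline LIC or ferritin measures the amount of iron, not whether it is being removed, so it may carry only part of that information.

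Two things are at stake. If baseline ICT use is prognostic beyond the terms already in the model, leaving it out makes the residual variance larger than it need be. And if the arms happen to differ in the share of chelated subjects, the planned model cannot correct for that in the data at hand. A covariate added after unblinding to deal with such a difference would be open to the charge of being data-driven.

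**Working it through.** **Terms in each iron analysis**

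| Analysis | Hb and T/W strata | Own baseline | Baseline ICT use |
|---|---|---|---|
| LIC change, SAP 10.4.10 | yes | yes | no |
| Ferritin change, ANCOVA, SAP 10.4.9 | yes | yes | no |
| Ferritin change, Wilcoxon fallback | no | no | no |
| LIC/ICT responder, SAP 10.4.8 | yes | not applicable | yes |

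**The plan's own figure.** There is no power, effect or SD for LIC or ferritin to reproduce. The only continuous endpoint with a power figure is NTDT-PRO T/W (SAP 4.4): difference 0.7, SD 1.2, 100 versus 50. SE = 1.2 × √(1/100 + 1/50) = 0.208; 0.7/0.208 = 3.37; power = Φ(3.37 − 1.96) = 92% (91.7% by noncentral t), against a stated 91%. It agrees closely but says nothing about the iron endpoints. Everything below therefore rests on assumed inputs.

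**Precision.** Let R² be the share of residual variance that baseline ICT use explains beyond the strata and the outcome's own baseline (assumption). A test with 80% power without the ICT term then has power Φ((1.96 + 0.842)/√(1 − R²) − 1.96) with it. The equivalent gain in sample size is 1/(1 − R²) − 1.

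| R² | Power with ICT term | Equivalent extra subjects |
|---|---|---|
| 0 | 80% | 0% |
| 0.05 | 82.0% | 5% |
| 0.10 | 84.0% | 11% |
| 0.15 | 86.0% | 18% |
| 0.20 | 87.9% | 25% |

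**Chance imbalance.** With a share p on ICT (assumption, 30% to 50%) and 90 versus 45 subjects after the planned 10% dropout, the SD of the between-arm difference in that share is √(p(1 − p)(1/90 + 1/45)) = 0.084 to 0.091. The 95% range is about ±16 to ±18 percentage points.

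An imbalance of k SDs moves the estimate by k√R² standard errors, because both the imbalance and the SE scale with √(1/n₁ + 1/n₀). For R² = 0.05 to 0.20, one SD of imbalance is worth 0.22 to 0.45 SE, and an imbalance at the edge of the 95% range is worth 0.44 to 0.88 SE. Given an imbalance at that edge, the false-positive rate is 1 − Φ((1.96 − 1.96√R²)/√(1 − R²)) + Φ((−1.96 − 1.96√R²)/√(1 − R²)) = 6.6% at R² = 0.05 and 11.4% at R² = 0.20.

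**Averaged over randomisation.** The ANCOVA was simulated with 10,000 runs per setting, 90 versus 45 subjects, two binary strata, and ICT use made more likely at higher baseline LIC.

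| ICT effect (residual SDs) | Type I error, ICT omitted | Power, ICT omitted | Power, ICT included |
|---|---|---|---|
| 0.25 | 5.1% | 80.8% | 81.0% |
| 0.5 | 5.4% | 79.5% | 81.1% |
| 1.0 | 5.4% | 73.0% | 81.1% |

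The mean treatment estimate was correct with and without the ICT term. The type I error differs from 5% by no more than simulation error (SE about 0.2 points).

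**The case against.** Three stronger readings are tempting, and the documents support none of them.

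- **The planned contrast is biased.** A reader might infer that an imbalance in chelation would be mistaken for a drug effect. Chance imbalance is part of the sampling variation that the test and interval already cover; the simulation shows an unbiased estimate and about 5% type I error. The 6.6% to 11.4% figures apply only to a trial that happens to have drawn an extreme imbalance.
- **The plan contradicts itself**, since the responder test adjusts for ICT and these models do not. The responder endpoint is itself defined partly by ICT. A dose reduction can occur only in someone already on ICT, and the rule for baseline LIC below 3 mg/g dw differs by ICT status. That is reason enough to stratify there, and it implies nothing about the change models.
- **At the same LIC, chelated subjects fall and unchelated subjects rise.** Nothing in the documents says so. Those on ICT at consent are on established treatment, and ICT may be started at any time during the study, so a baseline No need not mean unchelated at Week 24 or 48.

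It can also be said that treatment, strata and own baseline already make a complete, prespecified model, and that the same case could be made for splenectomy or transfusion burden. Nor is chelation neglected overall: SAP 10.4.7 analyses ICT dose change and summarises ICT use at baseline by arm, so an imbalance would probably be visible.

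All of that stands, and it limits the point to an optional improvement. It does not remove it. Seeing an imbalance is not adjusting for it, and this covariate, unlike most candidates, is already needed for a test in the same iron domain.

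**Conclusion.** The point holds as an improvement in precision and in protection against chance imbalance. It is not a finding of bias or invalidity. Both documents omit baseline ICT use from the LIC and ferritin ANCOVAs, and stratification does not balance it.

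The size cannot be determined from the documents, which give no ICT prevalence, no SD for LIC or ferritin, and no effect of ICT on either. If baseline ICT use explains a further 5% to 20% of variance, 80% power becomes about 82% to 88%. If it explains nothing beyond the outcome's own baseline, the gain is nil. The 80% starting point is itself only a reference value.

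LIC and ferritin change are other secondary endpoints outside the sequence in SAP 10.1, so the primary and key secondary conclusions are untouched. A baseline covariate also leaves open how to treat ICT started or changed after randomisation.

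**What to change.** Before unblinding:

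- Add baseline ICT use (Yes/No) as a covariate to the ANCOVAs in SAP 10.4.9 and 10.4.10, at Weeks 24 and 48, and align Protocol 9.6.3.9 and 9.6.3.10.
- Use the same derivation as the responder stratum in SAP 10.4.8, taken from the 24-week history, and write down the Yes/No rule. SAP 10.4.8 defines a baseline dose but does not say how to classify, for example, a subject who stopped ICT within the 24 weeks.
- Replace the Wilcoxon fallback for ferritin with an adjusted analysis carrying the same covariates, such as ANCOVA on log ferritin or rank ANCOVA. Otherwise the added covariate is lost whenever the fallback is used. SAP section 10 already allows log transformation for ANCOVA where needed, so the log-scale option fits the plan.

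The cost is a few lines of SAP text, one degree of freedom per model and no new data collection.

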10.4.11 Transfusion Free for 24 and 48 weeks

Proportion of subjects who receive no RBC transfusions from Week 1 to Week 24 will be summarized and compared between the 2 treatment groups using CMH test with randomization stratification factor(s) adjusted.

Similarly, proportion of subjects who receive no RBC transfusion from Week 1 to Week 48 will be compared between the 2 treatment groups using CMH test with randomization stratification factor(s) adjusted.

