- ¹¹ End of Study visit should occur after the study is unblinded (ie, 48 weeks after last subject received the first dose of IP), and, at the End of Trial as defined in Section 3.3, whichever occurs later. Or, at the time a subject discontinues from the study.
- ¹² Hepatitis B and C: perform HCV-RNA and HBsAG and/or HBV-DNA by central lab; local lab results are accepted only if central lab results are not available on time for eligibility evaluation.
- ¹³ Subjects are required to see the Investigator at least every 24 weeks to assess for malignancy and premalignancy, as per standard of care.
- ¹⁴ Visits at Weeks 13, 19, 24, 37, 42 and 48 in DBTP should occur only if a dosing visit is not scheduled within ± 7 days of those respective weeks. Week 120 visit might be performed in the DBTP or in the OLP, if applicable (see footnote 17).
- ¹⁵ Serum GDF11 and other related biomarkers sample collection at 9 weeks after last dose to be performed only if not performed at Dose 16, and not performed within the last 12 weeks.
- ¹⁶ Subjects on placebo who discontinued the treatment, but have been assessed as per protocol up to 48 weeks after the first dose of IP, and continued their participation in the PTFP until the time of unblinding, refer to Section 3.1.4, will perform Week -1 visit to re-assess some Inclusion/Exclusion criteria as per Section 3.1.3. Eligibility review/confirmation of selected Inclusion/Exclusion criteria will be performed by the Investigator using local lab data that will be reported in the eCRFs. Note: Week -1 assessments in the OLP can be performed up to pre-Dose 1 Day 1, if needed.
- ¹⁷ All subjects on luspatercept treatment at the time of unblinding, as well as subjects on placebo in the DBTP or in the PTFP at the time of unblinding, if eligible as per Section 3.1.3, can be treated with luspatercept in the OLP starting from Dose 1 Week N (N = number of weeks in the DBTP since Dose 1 Week 1).
- ¹⁸ For early discontinuation subjects, these parameters to be reported up to 48 weeks Post Dose 1 Day 1 or Week 9 post last dose whichever is the later date.

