6.4. Post-treatment Follow-Up Period

All subjects who discontinue the IP before the study is unblinded will move to the PTFP to be followed until the unblinding. After the study is unblinded, subjects who discontinue luspatercept

in the DBTP may continue 5 years from first dose of IP, or 3 years from last dose (whichever occurs later), to complete the Post-treatment Follow-up Period under the rollover protocol.

All subjects who discontinue luspatercept after the study is unblinded, during the OLP, will move to the PTFP to be followed until the End of Trial (see Section 3.3) and may continue 5 years from first dose of IP, or 3 years from last dose (whichever occurs later), to complete the Post-treatment Follow-up Period under the rollover protocol

An administrative window of ± 7 days is permitted for visits.

In particular, subjects who discontinue the IP before completing 48 weeks in DBTP should perform the following visits: at 9 weeks after last dose, Weeks 13, 19, 24, 37, 42, 48 after first dose, if not already performed these visits at these time-points during the DBTP, and every 24 weeks up to at least 5 years from first dose of IP, or 3 years from last dose (whichever occurs later)(see Table 3 and below for specific assessments to be performed at each visit).

All subjects regardless of treatment duration with IP should perform the following visits: at 9 weeks after last dose and every 24 weeks up to at least 5 years from first dose of IP, or 3 years from last dose (whichever occurs later)(see Table 3 and below for specific assessments to be performed at each visit).

All subjects in PTFP, regardless of treatment duration with IP, will perform the following assessments at the above indicated visits as outlined in the Table of Events (see Table 3), which includes but not limited to:

- Iron chelating therapies - record on ongoing basis, until 9 weeks after last dose (as detailed in Section 6.2)
- Post-treatment medications/therapies: such as surgery, radiation, systemic or any other therapy for the subject's disease - record on ongoing basis, until 9 weeks after last dose
- Post-treatment procedures - record on ongoing basis, until 9 weeks after last dose
- Transfusion assessment - record on ongoing basis, until 9 weeks after last dose (as detailed in Section 6.2)
- Adverse event assessment - record on an ongoing basis all AEs until 9 weeks after last dose, related SAEs to be reported until End of Study (refer to Section 10 for additional details)

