5.2.1. Intent-to-Treat Population

The intent-to-treat (ITT) population will consist of all randomized subjects regardless of whether or not the subject received IP. All efficacy analyses will be conducted for the ITT population and will be analyzed based on randomization treatment.

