10.6 Handling of Missing Data or Dropouts

10.6.1 Missing Data for non-QoL Assessment

In order to assess the robustness of the findings on the primary and key secondary endpoints of hemoglobin response and change from baseline, the missing values will be imputed as follows:

- For binary responder/non-responder values, the non-responder imputation (NRI) method is used for primary analysis. The NRI method classifies all subjects with missing data as non-

responders. The supportive/sensitivity analysis will include the complete case analysis. The complete case analysis excludes all subjects with missing data.

Tipping point analysis may be conducted for the primary efficacy endpoint if necessary. Different number of responders between luspatercept and placebo will be assessed until the study conclusion is changed. Each imputed value is initially imputed as a non-responder. The imputed values in the luspatercept group will remain as non-responders while the imputed values in the placebo group are replaced as a responder one at a time, therefore changing the number of responders between groups. Once all imputed values in the placebo group have been replaced with responder values, one of the imputed values in the luspatercept group is replaced with a responder while all the imputed values in the placebo group are reset to all non-responders. This process of changing each imputed non-responder to a responder one at a time continues until all the imputed values in the luspatercept and placebo groups are changed to responders.

In this way, every pair of imputations between the placebo and luspatercept groups will be assessed similarly, creating a matrix of all possible missing patterns. At each iteration, the statistical analysis is assessed to result in a significant or non-significant p-value, and the result of the analysis is recorded. A table will be provided to identify at what point to which the difference in responder status causes a directional shift in the study result.

- For continuous values, the complete case analysis is the primary analysis. The supportive/sensitivity analysis will use the postbaseline mean imputation, the baseline imputation or multiple imputation (MI) method.

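### The transfusion-free endpoints have no rule for subjects not followed to Week 24 or 48, and the plan is inconsistent about which transfusions are recorded and used

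*SAP*

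**What the plan says.** **Definition.** SAP 10.4.11 gives the 24-week endpoint as "Proportion of subjects who receive no RBC transfusions from Week 1 to Week 24 will be summarized and compared between the 2 treatment groups", and the 48-week endpoint as "proportion of subjects who receive no RBC transfusion from Week 1 to Week 48 will be compared between the 2 treatment groups". Protocol 9.6.3.11 is equivalent. Both use a stratified CMH test. Neither document states a minimum follow-up or says how to classify a subject whose observation ends before the window closes.

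**Population.** SAP 5.2.1: "All efficacy analyses will be conducted for the ITT population and will be analyzed based on randomization treatment". Early leavers therefore stay in the denominator.

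**Missing data.** SAP 10.6.1 says that for binary outcomes "the non-responder imputation (NRI) method is used for primary analysis". Its lead-in gives the purpose as "In order to assess the robustness of the findings on the primary and key secondary endpoints of hemoglobin response and change from baseline". The transfusion-free endpoints are not named.

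**Data used.** SAP Section 10 sets an efficacy cutoff at the earliest of death, study discontinuation, last dose + 20 days and data cutoff, and says that assessments before it serve the primary and secondary endpoints. The same section says that, for other efficacy endpoints, collected records are used as needed.

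**Recording.** Protocol 6.4, for the post-treatment period: "Transfusion assessment - record on ongoing basis, until 9 weeks after last dose". The iron chelation line has the same end point. Footnote 18 to Table 3 reads: "For early discontinuation subjects, these parameters to be reported up to 48 weeks Post Dose 1 Day 1 or Week 9 post last dose". The later of those two dates applies. SAP Section 10 agrees with the footnote.

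**The concern.** A transfusion log contains events only. A subject who withdraws at Week 6 without a transfusion leaves an empty log, not a visibly missing value. A program that looks for any transfusion between Week 1 and Week 24 finds none and returns transfusion-free, for 24 weeks and for 48. If the last dose + 20 cutoff is applied to transfusions, a subject who stops treatment, stays in the study and is transfused two months later can get the same result, because that transfusion falls outside the data used.

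The SAP handles incomplete observation for its other hemoglobin outcomes: missing response is non-response, and response duration is censored at the cutoff. Here the choice is left to whoever programs the table. It can move the reported rates by several points and, if losses differ between arms, move the treatment difference in either direction. It should be settled before anyone knows which way it goes.

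**Working it through.** **Figures in the plan.** The documents give no rate or power for the transfusion-free endpoints. The usable inputs are the 10% drop-out and the 100 vs 50 allocation (Protocol 9.3, SAP 4.4). The power statement they accompany, at least 99% for the primary endpoint at 50% vs 10%, reproduces: 99.98% with 100 and 50 subjects, 99.95% with 90 and 45. It does not bear on this endpoint.

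**Step 1: effect of the scoring rule.** Let p be the transfusion-free rate among subjects followed to the end of the window, and d the fraction lost earlier with no transfusion recorded.

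- Leavers scored as successes: p(1 − d) + d
- Leavers scored as failures: p(1 − d)
- Gap within an arm: d, whatever p is
- Gap in the between-arm difference: d(luspatercept) − d(placebo)

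At d = 10%, each arm's rate moves by 10 points. This treats the whole planned drop-out as lost before the window closes and untransfused, so it is an upper figure for that drop-out.

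Illustration with assumed p = 90% (luspatercept) and 75% (placebo), a 15-point difference among followed subjects:

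| Loss, luspatercept / placebo | Leavers as successes | Difference | Leavers as failures | Difference |
|---|---|---|---|---|
| 10% / 10% | 91.0 vs 77.5 | 13.5 | 81.0 vs 67.5 | 13.5 |
| 8% / 12% | 90.8 vs 78.0 | 12.8 | 82.8 vs 66.0 | 16.8 |
| 5% / 15% | 90.5 vs 78.75 | 11.75 | 85.5 vs 63.75 | 21.75 |
| 15% / 5% | 91.5 vs 76.25 | 15.25 | 76.5 vs 71.25 | 5.25 |

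With no true difference (90% in both arms) and losses of 5% vs 20%, success scoring gives 90.5 vs 92.0 (−1.5 points) and failure scoring gives 85.5 vs 72.0 (+13.5 points).

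**Step 2: how far the data reach after treatment stops.** With 21-day dosing and no delays, Dose k falls on Day 1 + 21(k − 1). Protocol 6.4 ends recording at last dose + 63 days. The efficacy cutoff can fall at last dose + 20 days.

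| Last dose | Day given | Recording ends (+63) | Cutoff (+20) |
|---|---|---|---|
| 1 | 1 | 64 | 21 |
| 5 | 85 | 148 | 105 |
| 6 | 106 | 169 | 126 |
| 7 | 127 | 190 | 147 |
| 8 | 148 | 211 | 168 |
| 13 | 253 | 316 | 273 |
| 14 | 274 | 337 | 294 |
| 15 | 295 | 358 | 315 |
| 16 | 316 | 379 | 336 |

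Against Day 168 (24 × 7) and Day 336 (48 × 7):

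- Protocol 6.4 falls short of Week 24 if the last dose is Dose 5 or earlier, and of Week 48 if it is Dose 13 or earlier. The gap is 20 days at each of those doses and longer for earlier ones (104 and 272 days at Dose 1).
- The cutoff falls short at Dose 7 or earlier for Week 24, and at Dose 15 or earlier for Week 48.
- Under footnote 18 there is no recording gap for subjects who stay in the study.

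The day convention matters. The hemoglobin window in SAP 5.1 ends Week 24 at Day 169, which implies Day 337 for Week 48 (169 + 168). On that convention the cutoff also misses by one day at Dose 8 (Day 168) and Dose 16 (Day 336).

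**The case against.** **The definition is silent, so a success rule cannot be attributed to it.** This stands. A reader might infer that the plan counts every early leaver as transfusion-free. No passage says that, and Protocol Table 2, which describes being transfusion-free over the period with occurrence assessed at every visit, fits an observed-status reading as well. SAP Section 10 also says that categorical comparisons follow the primary endpoint, which uses non-responder imputation. That sentence concerns the CMH comparison, however, and the lead-in to 10.6.1 names only hemoglobin endpoints. Non-responder scoring is therefore possible but not established.

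**The recording conflict is largely editorial.** Mostly fair. Section 6.4 refers the site to Table 3, whose transfusion row carries footnote 18, and SAP Section 10 agrees with the footnote. A reader might infer that sites will stop recording at 9 weeks, but that happens only if they follow 6.4 without the table. The wording still conflicts, and the list in 6.4 of extra assessments for early stoppers restores hemoglobin but not transfusions.

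**Failure scoring is not neutral.** This is right, and it limits the remedy. With 5% vs 15% loss, a 15-point difference among followed subjects becomes 21.75 in luspatercept's favour.

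**Two further inferences lack support.** The documents do not show that leavers would mostly be placebo subjects heading for transfusion. Nor are these endpoints shown to be the trial's only look at transfusion need: Protocol 6.8 evaluates the number of transfusion events, and some endpoint rows are redacted.

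**Conclusion.** The gap is real and should be closed, as a clarification with measurable consequences. The plan does not say how incomplete follow-up is scored for the two transfusion-free endpoints. Followed literally, it allows early leavers, and early stoppers transfused after last dose + 20, to count as transfusion-free.

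The choice between success and failure scoring is worth each arm's loss fraction on that arm's rate: up to 10 points at the planned drop-out. Its effect on the treatment difference is luspatercept loss minus placebo loss: zero with equal losses, 10 points in the 5% vs 15% example, and of the opposite sign if losses are reversed. The transfusion-free rates and unequal losses are assumptions; only the 10% drop-out is the plan's.

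Both are other secondary endpoints outside the gatekeeping sequence in SAP 10.1, so the primary and key secondary conclusions do not depend on the scoring rule.

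**What to change.** Before unblinding:

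1. **SAP 10.4.11, data used.** Use every recorded transfusion through the end of Week 24 or Week 48, regardless of the last dose + 20 cutoff, and state the last day. Day 169 would match the SAP's hemoglobin window for Week 24.
2. **SAP 10.4.11, classification.** Count a subject as transfusion-free only if followed to that day with none recorded, in line with the non-responder rule for hemoglobin response.
3. **Support.** Because failure scoring can enlarge the difference when placebo loss is higher, add a Kaplan-Meier analysis of time to first transfusion, censored at the last transfusion assessment, and a complete-case analysis of subjects followed to the stated day.
4. **Protocol 6.4.** Reconcile the transfusion and iron chelation lines with Table 3 footnote 18. The End of Study list in the same section gives yet another end point for iron chelation and should be aligned at the same time.

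The cost is a few sentences and two supportive analyses. No new visits are needed, because Protocol 6.4 already schedules early stoppers through Week 48. Compared with success scoring, reported transfusion-free rates would be somewhat lower.
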